#### 10.4.2.1.2 Nonhematologic Toxicities

Table 14 provides oprozomib dosing actions that should be taken for nonhematologic toxicities.

Approved

**Table 14 Guidelines for Dose Modification of Oprozomib/Placebo and Pomalidomide for Nonhematologic Toxicities**

Symptom	Findings	Recommended Action a	
		Oprozomib	Pomalidomide
Tumor Lysis Syndrome	Generally recognized in at least 3 or more of the following categories: (1) Increase in creatinine, uric acid, or phosphate of $\geq 50\%$ (2) Increase in potassium of $\geq 30\%$ (3) Decrease in calcium of $\geq 20\%$ , or (4) Increase in LDH $\geq 2$ -fold from baseline	Hold both oprozomib and pomalidomide until all abnormalities in serum chemistries have resolved to baseline; resume at full doses.	
Neuropathy	Grade 2 neuropathy with pain or $\geq$ Grade 3 neuropathy	Hold dose until toxicity resolves to $\leq$ Grade 1 or has returned to baseline. Resume study drug at 1 dose decrement.	Hold dose until toxicity resolves to $\leq$ Grade 1 or has returned to baseline. Resume study drug at 1 dose decrement from previous dose.
Infection	Grade 3 or 4	Hold both oprozomib and pomalidomide until systemic treatment for infection complete. If ANC $\geq 1.0 \times 10^9/L$ , resume both drugs at full dose. If ANC $< 1.0 \times 10^9/L$ , follow hematologic toxicities dose reduction guidelines (Table 13).	
Nausea, vomiting, diarrhea, or constipation	$\geq$ Grade 3 without optimal supportive care as defined by use of both a 5-HT 3 antagonist and aprepitant	Oprozomib-related: Full dose oprozomib but institute optimal supportive care.	Pomalidomide-related: Hold dose until toxicity resolves to $\leq$ Grade 1 or has returned to baseline. Resume study drug at 1 dose decrement from previous dose.
	$\geq$ Grade 3 with optimal supportive care as defined by use of both a 5-HT 3 antagonist and aprepitant	Oprozomib-related: Hold dose until toxicity resolves to $\leq$ Grade 1 or has returned to baseline. Resume study drug at 1 dose decrement.	
Fatigue	Grade 3 fatigue lasting $< 14$ days	Full dose.	Hold dose until toxicity resolves to $\leq$ Grade 1 or has returned to baseline. Resume study drug at 1 dose decrement from previous dose.
	Grade 3 fatigue lasting $\geq 14$ days	Hold dose until toxicity resolves to $\leq$ Grade 1 or has returned to baseline. Resume study drug at 1 dose decrement.	

Approved

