**Dose-Limiting Toxicities**

During this study, assessment of DLTs will occur during the 28-day period of Cycle 1 combination therapy. For the purposes of this study, a DLT is defined as any of the study drug-related events listed below occurring within the 4 weeks after the first dose of combination therapy. Study drug is defined as the combination of oprozomib, pomalidomide, and dexamethasone. Study drug-related is defined as a reasonable likelihood of clinical causality based on time of event, biology, dechallenge improvement, and that the adverse event (AE) was not likely explained by the subject's clinical state, underlying disease, concomitant medication, or study/nonstudy procedure.

- Any toxicity requiring a dose reduction or requiring that a dose of oprozomib or pomalidomide be held in Cycle 1 that does not meet the criteria for DLT will be discussed by the CSRC to determine whether the subject should be considered evaluable for DLT determination. If it is determined that the subject is not evaluable for DLT, the subject will be replaced.
- A delay in ability to receive Day 1 dose of Cycle 2 due to a hematologic or nonhematologic drug-related toxicity persisting beyond 14 days from Cycle 1 Day 28 will be considered a DLT

Approved

**Study design  
(cont'd):**

- For a nonhematologic DLT, any  $\geq$  Grade 3 toxicity will be considered a DLT with exceptions as described below:
    - Grade 3 asymptomatic electrolyte abnormalities will not be considered a DLT
    - Asymptomatic Grade 3 hypophosphatemia lasting less than 24 hours will not be considered a DLT
    - Grade 3 nausea and vomiting will not be considered a DLT unless persisting longer than 3 days despite optimal supportive care, which at a minimum must include a 5-hydroxytryptamine type-3 (5-HT3) antagonist and aprepitant
    - Grade 3 diarrhea will not be considered a DLT unless persisting longer than 3 days despite optimal supportive care, which at a minimum must include loperamide (Imodium) and atropine diphenoxylate (Lomotil)
    - Grade 3 fatigue lasting  $<$  14 days is not considered a DLT
    - $\geq$  Grade 3 hyperglycemia or toxicity attributed to dexamethasone is not considered a DLT
    - $\geq$  Grade 3 rash attributed specifically to pomalidomide is not considered a DLT
  - Hematologic DLTs consist of the following:
    - Grade 4 neutropenia:

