**Table 14 Guidelines for Dose Modification of Oprozomib/Placebo and Pomalidomide for Nonhematologic Toxicities (cont'd)**

Symptom	Findings	Recommended Action a	
		Oprozomib	Pomalidomide
Renal Dysfunction	CrCl 30 to < 50 mL/min (Grade 2)	Full dose.	Full dose.
	CrCl 15 to < 30 mL/min (Grade 3)	Hold dose. When CrCl recovers to ≤ Grade 2, resume at 1 dose decrement.	Hold dose. When CrCl recovers to ≤ Grade 2, resume dose at 1 dose decrement. If Grade 3 CrCl reappears, then hold dose until CrCl recovers to ≤ Grade 2 and reduce dose an additional 1 dose decrement.
	CrCl 0 to < 15 mL/min (Grade 4)	Discontinue.	Discontinue.
Elevation in Liver Function Tests	≥ Grade 3 (AST, ALT, or total bilirubin) b	Hold until resolves to baseline. Resume at 1 dose decrement.	Hold pomalidomide and restart treatment at 1 dose decrement less than the previous dose when toxicity has resolved to ≤ Grade 2 at physician discretion.
Other Nonhematologic Toxicity	Assessed as oprozomib-related and ≥ Grade 3 c	Hold oprozomib dose until toxicity resolves to ≤ Grade 1 or baseline; restart at 1 dose decrement.	Full dose.
Other Nonhematologic Toxicity	Assessed as pomalidomide-related and ≥ Grade 3 e,d	Full dose.	Hold pomalidomide and restart treatment at 1 dose decrement less than the previous dose when toxicity has resolved to ≤ Grade 2 at physician discretion.
Grade 1 or 2 GI hemorrhage	Assessed as oprozomib-related	DELAY until Grade 0 DECREASE one dose level for Grade 2	Full dose at physician discretion
Grade 3 or 4 GI Hemorrhage	Assessed as oprozomib-related	Discontinue.	Full dose when AE resolves to ≤ Grade 2 at physician discretion.

5-HT3 = 5-hydroxytryptamine type-3; AE = adverse event; ALT = alanine aminotransferase; ANC = absolute neutrophil count; AST = aspartate aminotransferase; CrCl = creatinine clearance; eCRF = electronic case report form; GI = gastrointestinal; LDH = lactate dehydrogenase; ULN = upper limit of normal.

a The maximum allowed dose interruption is 4 weeks for treatment-related toxicity.

b If AST or ALT is ≥ 3 × ULN, the “evaluation of treatment emergent liver abnormalities” eCRF should be completed.

c If cardiac or pulmonary treatment-emergent toxicities occur, the “cardiopulmonary AE” eCRF should be completed.

d See [Celgene Corporation, 2013](#).

Approved

Additional guidance regarding nonhematologic toxicities and dosing actions is as follows:

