## 10.5 DEFINITION OF DOSE-LIMITING TOXICITY

During this study, assessment of DLTs will occur during the 28-day period of Cycle 1 combination therapy. For the purposes of this study, a DLT is defined as any of the study drug-related events listed below occurring within the 4 weeks after the first dose of combination therapy. Study drug-related is defined as a reasonable likelihood of clinical causality based on time of event, biology, dechallenge improvement and that the AE was not likely explained by the subject's clinical state, underlying disease, concomitant medication, or study/nonstudy procedure.

- Any toxicity requiring a dose reduction or requiring that a dose of oprozomib or pomalidomide be held in Cycle 1 that does not meet the criteria for DLT will be discussed by the CSRC to determine whether the subject should be considered evaluable for DLT determination. If it is determined that the subject is not evaluable for DLT, the subject will be replaced.
- A delay in ability to receive Day 1 dose of Cycle 2 due to a hematologic or nonhematologic drug-related toxicity persisting beyond 14 days from Cycle 1 Day 28 will be considered a DLT
- For a nonhematologic DLT, any  $\geq$  Grade 3 toxicity will be considered a DLT with exceptions as described below:
  - Grade 3 asymptomatic electrolyte abnormalities will not be considered a DLT
  - Asymptomatic Grade 3 hypophosphatemia lasting less than 24 hours will not be considered a DLT
  - Grade 3 nausea and vomiting will not be considered a DLT unless persisting longer than 3 days despite optimal supportive care, which at a minimum must include a 5-hydroxytryptamine type-3 (5-HT3) antagonist and aprepitant
  - Grade 3 diarrhea will not be considered a DLT unless persisting longer than 3 days despite optimal supportive care, which at a minimum must include loperamide (Imodium) and atropine diphenoxylate (Lomotil)
  - Grade 3 fatigue lasting < 14 days is not considered a DLT
  - $\geq$  Grade 3 hyperglycemia or toxicity attributed to dexamethasone is not considered a DLT (see dose reduction guidelines for dexamethasone in [Section 10.4.1](#))
  - $\geq$  Grade 3 rash attributed specifically to pomalidomide is not to be considered a DLT

Approved

CONFIDENTIAL

- Hematologic DLTs consist of the following:
  - Grade 4 neutropenia:
    - Absolute neutrophil count (ANC)  $< 0.5 \times 10^9/L$  lasting  $\geq 7$  days despite adequate growth factor support (eg, G-CSF)

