#### **10.6.1.2 Antinausea and Antiemetics**

It is strongly recommended that subjects be premedicated with a 5-HT3 inhibitor, such as ondansetron or granisetron, prior to administration of the first dose of oprozomib each day

Approved

and throughout the day as needed to prevent nausea and vomiting. If nausea/vomiting at any grade persists, aprepitant or fosaprepitant is recommended. Additional antiemetics may be used per investigator discretion.

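### Table 14 judges supportive care for diarrhea by antiemetics, so Grade 3 or higher diarrhea that has failed both antidiarrheals is first directed to full-dose oprozomib

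*Protocol*

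**What the plan says.** Section 10.4.2.1.2 introduces the table with "Table 14 provides oprozomib dosing actions that should be taken for nonhematologic toxicities". Table 14 then has a single row for nausea, vomiting, diarrhea and constipation, with two branches, both for events of Grade 3 or higher. The first covers an event "without optimal supportive care as defined by use of both a 5-HT 3 antagonist and aprepitant", and its action for an oprozomib-related event is "Full dose oprozomib but institute optimal supportive care". The second covers the same event in a subject who is on both drugs; oprozomib is held until recovery to Grade 1 or baseline and resumed one decrement lower. The row names no antidiarrheal.

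Section 10.5 and the synopsis treat the symptoms separately. For nausea and vomiting the minimum care is a 5-HT3 antagonist plus aprepitant. For diarrhea the synopsis says "Grade 3 diarrhea will not be considered a DLT unless persisting longer than 3 days despite optimal supportive care", and Section 10.5 specifies care "which at a minimum must include loperamide (Imodium) and atropine diphenoxylate (Lomotil".

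The concomitant medication sections follow the same division. Section 10.6.1.3 advises loperamide at the onset of diarrhea and Lomotil if it persists. Section 10.6.1.2 strongly recommends a 5-HT3 inhibitor before the day's first oprozomib dose and adds "If nausea/vomiting at any grade persists, aprepitant or fosaprepitant is recommended". It gives no role for aprepitant in diarrhea.

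**The concern.** A dose-modification rule should turn on whether the treatment for that toxicity has been tried. For diarrhea, Table 14 turns on whether two antiemetics have been given. A subject whose severe diarrhea has already failed the only antidiarrheal regimen the protocol defines can therefore be classed as not yet on optimal care and kept at full dose.

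This matters because Section 3.5.2 reports GI events as the most frequent with oprozomib. Sections 3.4.2.2 and 3.5.1 list Grade 3 diarrhea as a single-agent DLT on the 2/7 schedule, although at 330 mg, which is above the 300 mg MTD and above the illustrative 210 to 270 mg cohorts here. SAP Section 2.1 names GI tolerability among three concerns identified before Part 2 was cancelled. Table 14 also applies in every cycle, not only in the DLT window.

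**Working it through.** No arithmetic applies and the plan states no figure on this point. The check is to trace one subject through the sections. The subject has oprozomib-related diarrhea of Grade 3 or 4, is taking loperamide and diphenoxylate/atropine, has 5-HT3 premedication, and is not on aprepitant.

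1. **Can this state arise under the protocol?** Yes. Section 10.6.1.3 leads to both antidiarrheals. Section 10.6.1.2 brings in aprepitant only for persistent nausea or vomiting, so a subject with diarrhea alone has no reason to receive it.

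2. **Table 14 as written.** The branch condition needs both antiemetics. Aprepitant is missing, so the first branch applies: full dose, and start optimal supportive care. Within this row that care means the antiemetic pair, so the step prescribed is to add aprepitant.

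3. **What follows.** If the diarrhea is still Grade 3 or higher once the subject is on both antiemetics, the second branch applies: hold, then resume one decrement lower.

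4. **The same subject under the Section 10.5 diarrhea definition.** Optimal supportive care is already in place, so the second branch applies at once. The two definitions give different oprozomib actions for the same event.

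5. **Grade.** The row starts at Grade 3 and has no upper limit, so Grade 4 diarrhea takes the same route. The Section 10.5 exception covers Grade 3 only. In Cycle 1, study drug-related Grade 4 diarrhea is therefore a DLT whatever its duration, and Grade 3 diarrhea lasting more than 3 days on both antidiarrheals is also a DLT. One event can count as dose-limiting for the cohort while the dosing table directs full dose for the subject.

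6. **The table's own default.** For other oprozomib-related nonhematologic toxicity of Grade 3 or higher the action is "Hold oprozomib dose until toxicity resolves to" Grade 1 or baseline, with restart one decrement lower. Diarrhea has its own row, so this default does not reach it.

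7. **The opposite mismatch.** A subject already on both antiemetics but on no antidiarrheal goes straight to hold-and-reduce. That is cautious, but it confirms that the branch does not depend on whether diarrhea has been treated.

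8. **Constipation.** It sits in the same row under the same antiemetic condition. Section 10.6.2 already allows laxatives as needed, and the row does not mention them.

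**The case against.** The strongest reply is that the full-dose cell has a second half. It also tells the site to start optimal supportive care, so the branch is a transition to hold-and-reduce. That stands. A reader might infer that Table 14 keeps such a subject at full dose indefinitely; the text does not support this. The remaining fault is that the step interposed before the hold is an antiemetic, which is not part of the protocol's care for diarrhea.

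A second reply is that the table is guidance. Its column is headed as recommended action. Section 10.4 allows permanent discontinuation on the investigator's judgment and written exceptions from the medical monitor, Section 10.4.1 allows interruption for treatment-related toxicity, and Section 10.4.2.1.2 says oprozomib should be discontinued if toxicity continues. These provisions soften the harm. None of them supplies a diarrhea definition for the table, and Section 10.4.2.1.2 presents the actions as ones that should be followed.

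A third reply is that full dose at Grade 3 is a deliberate tier in Table 14. Grade 3 fatigue under 14 days also continues at full dose, in line with "Grade 3 fatigue lasting < 14 days is not considered a DLT" in Section 10.5. That is fair, and the tier itself is not the complaint. The complaint is the condition that places treated diarrhea in it.

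A fourth reply is that the dosing tables and the DLT definition differ elsewhere. Table 13 uses a fever threshold of 38.5°C on Day 1 where Section 10.5 uses 38.3°C, and Table 14 has no counterpart to the DLT exemption for asymptomatic Grade 3 electrolyte abnormalities. So agreement on other symptoms cannot prove a drafting slip. The conflict over diarrhea stands whatever its origin.

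Finally, Section 3.5.2 expects less GI toxicity when oprozomib is given with antimyeloma doses of dexamethasone. That bears on how often the case would arise, not on what the table says when it does.

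**Conclusion.** The point holds as an internal conflict with a safety consequence. For oprozomib-related diarrhea of Grade 3 or higher despite both antidiarrheals and without aprepitant, Table 14 directs full-dose oprozomib while antiemetics are added, where the protocol's own diarrhea definition would lead directly to hold-and-reduce. It should be fixed, but it is not grave.

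Its size cannot be put as a rate, because the documents do not give the frequency of this state. A reader might try to count the planned doses given at full strength before the hold. The documents do not say how soon the antiemetics must be started or when they are judged to have failed, so any such count would rest on an assumed delay.

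A reader might also infer that the MTD or the analyses are compromised. They are not on this ground: the DLT rule in Section 10.5 has the correct diarrhea definition, and no analysis population or sample size depends on Table 14.

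The conclusion rests on reading the row literally and on the Section 10.5 definition being the intended one for diarrhea. That definition was written for DLT classification, but it is the only diarrhea-specific one in the protocol, and Section 10.6.1.3 names the same two drugs. The note at the front of the protocol says Amendment 3 was approved but not implemented. The change logs show no edit to this row in Amendment 2 or 3, so it was probably in force earlier, although those logs show selected text only.

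**What to change.** Split the Table 14 row by symptom:

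- **Nausea and vomiting:** keep the 5-HT3 antagonist plus aprepitant definition.
- **Diarrhea:** define optimal supportive care as loperamide plus diphenoxylate/atropine, matching Section 10.5 and the synopsis.
- **Constipation:** remove the antiemetic condition; laxatives are already allowed under Section 10.6.2.

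The cost is a wording change to one table row, with no new data or procedures. Because Amendment 3 was not implemented, the practical use is in any later protocol that reuses this table. The split alone would leave Grade 4 diarrhea in a subject not yet on both antidiarrheals in a full-dose branch. Whether that tier should stop at Grade 3 is a separate clinical decision, which could be taken in the same edit.

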**Table 14 Guidelines for Dose Modification of Oprozomib/Placebo and Pomalidomide for Nonhematologic Toxicities (cont'd)**

Symptom	Findings	Recommended Action a	
		Oprozomib	Pomalidomide
Renal Dysfunction	CrCl 30 to < 50 mL/min (Grade 2)	Full dose.	Full dose.
	CrCl 15 to < 30 mL/min (Grade 3)	Hold dose. When CrCl recovers to ≤ Grade 2, resume at 1 dose decrement.	Hold dose. When CrCl recovers to ≤ Grade 2, resume dose at 1 dose decrement. If Grade 3 CrCl reappears, then hold dose until CrCl recovers to ≤ Grade 2 and reduce dose an additional 1 dose decrement.
	CrCl 0 to < 15 mL/min (Grade 4)	Discontinue.	Discontinue.
Elevation in Liver Function Tests	≥ Grade 3 (AST, ALT, or total bilirubin) b	Hold until resolves to baseline. Resume at 1 dose decrement.	Hold pomalidomide and restart treatment at 1 dose decrement less than the previous dose when toxicity has resolved to ≤ Grade 2 at physician discretion.
Other Nonhematologic Toxicity	Assessed as oprozomib-related and ≥ Grade 3 c	Hold oprozomib dose until toxicity resolves to ≤ Grade 1 or baseline; restart at 1 dose decrement.	Full dose.
Other Nonhematologic Toxicity	Assessed as pomalidomide-related and ≥ Grade 3 e,d	Full dose.	Hold pomalidomide and restart treatment at 1 dose decrement less than the previous dose when toxicity has resolved to ≤ Grade 2 at physician discretion.
Grade 1 or 2 GI hemorrhage	Assessed as oprozomib-related	DELAY until Grade 0 DECREASE one dose level for Grade 2	Full dose at physician discretion
Grade 3 or 4 GI Hemorrhage	Assessed as oprozomib-related	Discontinue.	Full dose when AE resolves to ≤ Grade 2 at physician discretion.

5-HT3 = 5-hydroxytryptamine type-3; AE = adverse event; ALT = alanine aminotransferase; ANC = absolute neutrophil count; AST = aspartate aminotransferase; CrCl = creatinine clearance; eCRF = electronic case report form; GI = gastrointestinal; LDH = lactate dehydrogenase; ULN = upper limit of normal.

a The maximum allowed dose interruption is 4 weeks for treatment-related toxicity.

b If AST or ALT is ≥ 3 × ULN, the “evaluation of treatment emergent liver abnormalities” eCRF should be completed.

c If cardiac or pulmonary treatment-emergent toxicities occur, the “cardiopulmonary AE” eCRF should be completed.

d See [Celgene Corporation, 2013](#).

Approved

Additional guidance regarding nonhematologic toxicities and dosing actions is as follows:

- Nontreatment-related events: If the toxicity resolves to  $\leq$  Grade 1 or baseline and the toxicity is not treatment-related, oprozomib may be restarted at the same dose level
- If the subject tolerates the reduced dose for 1 cycle, the subject's dose may be re-escalated to the dose being taken prior to the dose reduction
- If required by continued or recurrent toxicity, a second or third dose reduction of oprozomib may be permitted after discussion with the **Sponsor's** study medical monitor. No more than 3 dose reductions down to a minimum of 150 mg will be permitted for an individual subject on study and additional reductions will be managed by schedule change. If toxicity continues, oprozomib should be discontinued.
- Subjects who develop Grade 3 or 4 GI hemorrhage should not be rechallenged with oprozomib. Oprozomib should be permanently discontinued. Endoscopy should be strongly considered for any subject with GI hemorrhage.

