##### **Amendment 2:**

1. To allow subjects with prior carfilzomib exposure to be considered for inclusion in the study, if carfilzomib was not withdrawn due to toxicity.
2. To allow subjects with prior pomalidomide exposure to be considered for inclusion in the dose-escalation portion of the study, if pomalidomide was neither dose-reduced nor withdrawn due to toxicity.
3. To specify that only subjects who have been treated with adequate alkylator therapy are eligible to be considered for inclusion in the Phase 1b dose-escalation portion and Phase 3 portion of the study.
4. Additional safety guidance regarding Grade 3 or 4 GI hemorrhage (see [Section 10.4.2.1.2](#)), mandatory proton-pump inhibitors (see [Section 10.6.1.5](#)), and the addition of an exclusion criterion for patients with prior clinically significant

Approved

bleed in the 6 months prior to first dose of study treatment, because of toxicities observed in Study 2011-001.

5. Revisions in synopsis, statistical sections, objectives, and endpoints for accuracy, clarity, and consistency within the protocol.

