### 13.2 CAUSALITY

A suspected adverse event means any AE for which there is reasonable possibility that the study drug caused the AE. “Reasonable possibility” means that there is evidence to suggest a causal relationship between the drug and the AE.

The relationship of the AE to the study drug should be assessed using the following criteria:

YES; the event is suspected to be related if:

- There is a clinically plausible time sequence between the AE onset and administration of study treatment; and/or
- There is a biologically plausible mechanism for the study treatment to cause or contribute to the AE; and/or
- The event improves or diminishes upon withdrawal of the study drug without the initiation of any specific treatment for the event (dechallenge) and/or recurs or worsens with rechallenge (when clinically feasible); and/or
- The AE cannot be reasonably attributed to concurrent or underlying illness, other drugs, or procedures

NO; the event is not suspected to be related if:

- The AE is more likely to be explained by the subject’s clinical state, underlying disease, or concomitant medical, study, or nonstudy procedure; and/or
- The time of occurrence of the AE is not reasonably related to administration of study treatment; and/or
- The event is not related to the investigational product(s)

In the event of a possible drug-related AE, the investigator should to the best of his/her ability assess its relationship to each of the study drugs: oprozomib, pomalidomide, and dexamethasone.

Approved

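### Protocol Section 10.4.2.1.2: for a resolved Grade 3 or 4 GI hemorrhage unrelated to treatment, one bullet permits restarting oprozomib, another forbids it, and no precedence is stated

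*Protocol*

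**What the plan says.** Three current instructions in Protocol Section 10.4.2.1.2 bear on oprozomib after a Grade 3 or 4 GI hemorrhage.

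- **Last bullet of the additional guidance:** "Subjects who develop Grade 3 or 4 GI hemorrhage should not be rechallenged with oprozomib. Oprozomib should be permanently discontinued". Cause is not mentioned.
- **First bullet of the same list, on events not related to treatment:** after resolution to Grade 1 or lower or to baseline, and if "the toxicity is not treatment-related, oprozomib may be restarted at the same dose level". GI hemorrhage is not excepted.
- **Table 14, GI hemorrhage row:** "Grade 3 or 4 GI Hemorrhage Assessed as oprozomib-related Discontinue". The pomalidomide cell of that row reads "Full dose when AE resolves to ≤ Grade 2 at physician discretion".

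The Amendment 2 summary in Section 3.1 lists "Additional safety guidance regarding Grade 3 or 4 GI hemorrhage" among its purposes and says that it and related measures were introduced "because of toxicities observed in Study 2011-001".

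**The concern.** The last bullet is a safeguard against giving oprozomib again after a serious GI bleed. The first bullet, three items above it, grants permission to do so when the bleed is thought unrelated to treatment. It asks for no approval: the third bullet requires discussion with the medical monitor before a second or third dose reduction, but the first requires none before a restart.

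An unrelated attribution is possible. Section 10.6.1.6 makes an antiplatelet or anticoagulant mandatory while pomalidomide is taken, so an investigator has a ready explanation outside the study drugs.

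What is at stake is re-exposure of an individual subject. GI bleeding has been fatal with this drug elsewhere. Section 3.4.2.2 reports two Grade 5 GI hemorrhages at 240 mg on the 5/14 schedule, and Section 3.4.2.1 reports one Grade 5 upper GI hemorrhage at 210 mg with split dosing. These events show why a stopping rule exists. Neither section describes re-exposure after a bleed, so they do not measure the harm from a restart.

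**Working it through.** No arithmetic applies. The check sets the instructions side by side for each possible attribution of a Grade 3 or 4 GI bleed that has resolved.

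It needs a meaning for treatment-related. Section 5.1.3 defines study drug as the three-drug combination, and Section 14.5.1.1 lists oprozomib, pomalidomide and dexamethasone as study treatment. Section 13.2 asks the investigator to "assess its relationship to each of the study drugs: oprozomib, pomalidomide, and dexamethasone". A bleed attributed to any one of the three is therefore taken as treatment-related.

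| Bleed attributed to | First bullet | Last bullet | Table 14, GI hemorrhage row | Result |
|---|---|---|---|---|
| Oprozomib | Does not apply | Stop for good | Stop | Agreement |
| Pomalidomide or dexamethasone only | Does not apply | Stop for good | Silent | Only the last bullet speaks |
| No study drug | Restart allowed, same dose | Stop for good | Silent | Conflict |

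The next question is whether anything ranks the two bullets in the third line.

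- The sentence introducing the bullets calls them additional guidance and gives no order among them.
- Section 10.4 has a general discontinuation rule, but it covers only treatment-related toxicity, so it does not reach an unrelated bleed.
- Section 10.4 also allows exceptions with the medical monitor's written approval. That is a case-by-case route, not a rule of precedence.
- The SAP contains no dose-modification rules. Its Section 7.4.1 only summarizes modifications from adverse event action data.

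No ranking was found. The conflict is real, and it occurs in one attribution category of the three.

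For the MTD, Section 10.5 counts only study drug-related events as DLTs. An unrelated bleed is not a DLT under either bullet.

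**The case against.** The best reply is that the two bullets can both be obeyed. The first is general and only permits; the last names the event and prohibits. A site that follows the last bullet breaches nothing, and anyone reading the four-item list sees both. This stands as an account of what was probably intended. It does not make the text consistent, because the protocol never says that the specific rule prevails and the permission is written without an exception.

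A second reply is that the case will be uncommon and would be noticed. The criteria for relatedness in Section 13.2 are broad and joined by and/or, so few bleeds may end up unrelated. Restart must wait for resolution. SAEs are reported within 24 hours (Section 13.5), and the CSRC monitors safety in both escalation and expansion (Section 14.3). This also stands, and it is why the consequence is modest. None of these safeguards settles which bullet applies.

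A third reply is that the program was terminated, as the opening statement on amendments records. That reduces the practical urgency but leaves the wording as it is.

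**Conclusion.** The point holds in a narrow form. For a resolved Grade 3 or 4 GI hemorrhage judged unrelated to all three study drugs, the first and last bullets of Section 10.4.2.1.2 give opposite answers about oprozomib, and precedence is not stated. The wording mismatch is certain. How often it would arise is unknown, because the documents do not break Grade 3 or 4 GI hemorrhage down by attribution. It is a safety-wording defect with no bearing on the MTD rules, sample size or power. The conclusion assumes that treatment-related means related to any of the three drugs.

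A reader might infer two stronger points that the documents do not support.

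- **That Table 14 contradicts the last bullet.** The GI hemorrhage row gives an action for oprozomib-related bleeds and says nothing about others. A bullet that goes further adds to the row; it does not oppose it.
- **That a bleed attributed to pomalidomide falls under the Other Nonhematologic Toxicity row, "Assessed as pomalidomide-related and ≥ Grade 3", where oprozomib continues at full dose.** GI hemorrhage has rows of its own, so Other naturally leaves it out. The companion Other row, for oprozomib-related toxicity of Grade 3 or higher, says to hold oprozomib and restart one decrement lower. If Other included GI hemorrhage, Table 14 would tell sites both to restart and to discontinue oprozomib for the same oprozomib-related bleed.

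**What to change.** Add to the bullet on events not related to treatment: *except Grade 3 or 4 GI hemorrhage, after which oprozomib is permanently discontinued regardless of attribution*. That clause alone removes the conflict, and it adopts the stricter rule already written.

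Optionally, for consistency, add a footnote to the Grade 3 or 4 GI hemorrhage row of Table 14 stating that the oprozomib action applies whatever the attribution. Leave the pomalidomide cell unchanged.

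The opposite edit, limiting the last bullet to oprozomib-related bleeds, would also end the conflict. It would do so by loosening a safeguard that the sponsor introduced in response to observed toxicity, so it is not recommended.

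The cost is one clause, or one clause and a footnote. A few subjects with clearly unrelated bleeds would lose oprozomib, with the written-exception route in Section 10.4 still open to them.
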